### 1.3.2 Risk with Radiation Therapy (RT)

Radiation therapy is a standard treatment modality for GBM patients and has been established to be generally safe and well tolerated. However, the risk of radiation necrosis and other adverse events listed below may be increased with hypofractionated radiation therapy due to the increased dose given per fraction in hypofractionated prescriptions. However, in recent years, a number of small phase I and II studies and one large phase III trial have reported hypofractionated RT regimens to be well tolerated and result in similar early- and delayed-RT adverse effect profiles compared to standard radiotherapy regimens in selected newly diagnosed GBM patients.

Expected acute radiation therapy adverse events include skin reaction, including dryness, redness, itching (pruritis), tanning, soreness and hair loss, fatigue, nausea, vomiting, dry mouth, altered taste, decrease in blood counts, short-term hearing impairment due to reactions in the ear canals and on the ear, serous otitis media (fluid in the middle ear) as well as temporary aggravation of brain tumor symptoms such as headaches, seizures, and weakness.

Expected early delayed radiation therapy adverse events (occurring 1-3 months after radiotherapy treatment) include fatigue, lethargy and transient worsening of existing neurological deficits.

Expected late delayed radiation therapy adverse events (occurring 3 months or more after radiation therapy treatment) include radiation necrosis (severe local damage to normal brain tissue), which may result in permanent neurocognitive deficits (difficulties with short term memory, calculations, language and more severe neurocognitive deficits) or motor dysfunction, leukoencephalopathy, permanent hearing impairment, radiation injury to the visual structures including the optic nerve and chiasm, which can result in partial or complete blindness, cataracts endocrine dysfunction and radiation-induced neoplasms. Radiation necrosis can mimic recurrent brain tumor and may require surgery for diagnosis and treatment.

To minimize risk to the subject, modern RT techniques will be used including fractionated stereotactic radiotherapy, protons, and IMRT, which allow for highly conformal treatment to a considerably more precise target volume. These technologies have the potential to significantly reduce the toxicity associated with hypofractionated radiation.

### 1.3.3 Potential Overlapping Toxicities with Immunotherapy and Radiation Therapy

There is a theoretical risk that immunotherapy may potentiate the effects of central nervous system radiation necrosis given that radiation-related central nervous system necrosis is partially immune-mediated. Thus, there is potential for increased frequency of cerebral radiation necrosis and severe

CONFIDENTIAL

This material is the property of the NYU School of Medicine. Do not disclose or use except as authorized in writing by the study sponsor

neurotoxicity from cerebral radiation necrosis. This potential for overlapping toxicity may also result in an increased risk of surgery for diagnosis and treatment of radiation necrosis.

However, a recent phase I study has demonstrated that hypofractionated re-irradiation can be safely combined with immune checkpoint therapy in recurrent high-grade glioma patients and a retrospective study has reported that immune checkpoint therapy can be safely combined with various hypofractionated radiation prescriptions in melanoma brain metastasis patients.

Therefore, we will conduct a Safety Lead-in (see Section 6.1.1 for details) that will include the first 6 subjects to further define the safety and tolerability of nivolumab and ipilimumab when combined with hypofractionated RT in newly diagnosed GBM subjects. Furthermore, we will conduct a special interim safety analysis for evaluation of late delayed radiation therapy adverse events due to the possibility of increased incidence of CNS toxicity from delayed radiation necrosis or radiation injury (see Section 3.5.2 for details).

#### 1.3.4 Other Risks of Study Participation

Beyond the risk of study therapy exposure, subjects will not be exposed to additional risk beyond the risks associated with standard of care safety procedures for GBM therapy. The study procedures including subject visits, vital signs, phlebotomy approximately every 2 weeks, and imaging/response assessments approximately every 2 months, are equivalent to the procedures that would be performed for standard therapy for GBM. Alternative courses of management would be standard therapy with conventional fractionated radiation therapy alone, conventional fractionated radiotherapy with concurrent temozolomide chemotherapy, and no interventional therapy with palliative care only. With the study regimen, there is likely reduced risk of neurotoxicity and myelotoxicity compared to standard therapy for GBM since the study regimen consists of lower doses of radiotherapy than standard therapy regimens and does not contain a cytotoxic chemotherapy regimen.

The prognosis is so poor in newly diagnosed GBM with unmethylated *MGMT* with the standard regimen that palliative care only is considered a reasonable approach for many patients. Compared to palliative care, the risks associated with study participation outside of study therapy exposure include the risk of phlebotomy, imaging response assessments including cranial MRI, and visits with practitioners. Risks associated with phlebotomy include weakness, redness, pain, bruising, bleeding, or infection at the needle site. To minimize risk, patients will be counseled on study procedures and associated risks throughout the duration of the study.

Risk of harm from genetic testing may be a possibility should the principal investigator identify important findings in the future research and the subject opt into receiving these results. Genetic testing can generate information about a subjects' personal health risks and can cause or increase anxiety, damage family relationships, and/or compromise insurability, employability and can even lead to discrimination. Results will only be disclosed by a qualified genetic counselor under the circumstance that the PI believes they are important for the subject's health, and results will not be shared with employers, insurers, or placed in the subject's medical record, thereby greatly reducing the possibility of psychological or social risks that could arise from knowledge of this genetic information, such as risk for employability or insurability or the risk of discrimination. Additional risks to study participation include breach of confidentiality. Privacy procedures in place and good clinical practice guidelines are followed for the study to minimize risks associated with research procedures and participation.

#### 1.3.5 Potential benefits

The potential benefits to subjects with study participation are improved tumor control and improved overall survival with study participation. With standard regimens, the median survival is poor for patients with GBM with unmethylated *MGMT*, and palliative care only is considered a reasonable approach for these patients.

CONFIDENTIAL

This material is the property of the NYU School of Medicine. Do not disclose or use except as authorized in writing by the study sponsor

## 2 Study Objectives

### 2.1 Research Hypothesis

This study will test the hypothesis that hypofractionated radiotherapy (45 Gy in 15 fractions) will result in reduced treatment-induced severe lymphopenia compared to standard chemoradiation and enhance the efficacy of combination immune checkpoint therapy to improve the survival of newly diagnosed *MGMT*-unmethylated glioblastoma (GBM) subjects.

### 2.2 Overall Study Objectives

#### Main Study Cohort:

- The primary objective of this open-label, phase II trial will be to determine the overall survival at 1 year (1-yr OS) of adults with newly diagnosed, *MGMT* unmethylated GBM administered nivolumab, ipilimumab and hypofractionated RT.
- Secondary objectives will be to evaluate the safety and tolerability and to estimate additional measures of efficacy, as outlined in the study endpoints.

#### Surgical Study Cohort:

- The primary objective is to assess safety, feasibility and tolerability
- Secondary objectives will be to estimate measures of efficacy, as outlined in the study endpoints.

#### Both Study Cohorts:

We will explore the association of 1-yr OS with tumor tissue and circulating biomarkers as described in the exploratory study endpoints to identify potential biomarkers that predict response or resistance.

## 3 Study Design

### 3.1 General Design

[figure not shown]
#### 3.1.1 Study Schema

#### Timeline of Selected Important Events

[figure not shown]
CONFIDENTIAL

This material is the property of the NYU School of Medicine. Do not disclose or use except as authorized in writing by the study sponsor

### Main Study Cohort

### Surgical Study Cohort

### 3.1.2 General Study Design

This is an open label, phase II trial of nivolumab, ipilimumab and hypofractionated radiation therapy in adult patients with newly diagnosed, *MGMT* unmethylated GBM with the primary objective of determining the overall survival at 1 year.

**Safety Lead In:** The study will start with a Safety Lead-In consisting of the first 6 subjects (Section 6.1.1), which will be conducted to further define the safety and tolerability of nivolumab and ipilimumab when given in combination with hypofractionated radiotherapy in previously untreated, newly diagnosed GBM patients with unmethylated *MGMT* promoter. Note, special safety provisions are included for the first 3 subjects enrolled (see Section 6.1.1). After the first 6 subjects are enrolled, enrollment will stop and subjects will be observed for 40 days for dose-limiting toxicities (DLTs, see DLT definitions is Section 6.1.1.1). After all subjects in the Safety Lead-In cohort have completed the DLT observation period, the safety data will be reviewed by the Sponsor and the NYU DSMC. If 2 or more of the first 6 subjects in the Safety Lead-in experiences a DLT during the 40 day DLT observation period, the sponsor and the FDA, may redesign the dosing and schedule of the study treatment or will stop the study for unacceptable toxicity. If 1 or less of the first 6 subjects experiences a DLT at the end of the 28 day DLT observation period, the study will continue enrollment onto the phase II part of the study.

**Main Study Cohort:** The Phase II trial is an open-label, single-stage study at the nivolumab and ipilimumab doses and schedules determined to be safe in combination with RT in the Safety Lead-in.

The phase II trial will enroll a total of 24 subjects, including those from the safety lead-in. Monitoring of toxicity attributable to study treatment will be continually assessed during the phase II trial using a

CONFIDENTIAL

This material is the property of the NYU School of Medicine. Do not disclose or use except as authorized in writing by the study sponsor

Bayesian monitoring approach, assessing safety with the accrual of every three additional patients (see Primary Safety Endpoints, Section 3.5).

Surgical Study Cohort: We will use a single stage design to assess safety, feasibility and therapeutic efficacy of nivolumab and ipilimumab with the first dose being administered pre-operatively and continued post-operatively in conjunction with HFRT. We will enroll 16 subjects in this cohort. Monitoring of toxicity attributable to study treatment will be continually assessed (see Primary Safety Endpoints, Section 3.5).

### 3.1.3 General Overview Study Procedures

**All Subjects:** After screening procedures and registration, within 6 weeks of the first diagnostic neurosurgical procedure, all subjects will initiate study treatment with one dose of nivolumab IV (3 mg/kg) followed by one dose of ipilimumab IV (1 mg/kg).

#### **Safety Lead-In/Main Study Cohort:**

On C1D8, seven days after nivolumab and ipilimumab administration, all subjects will be administered radiotherapy (RT) to a total dose of 45 Gy, given in 15 consecutive fractions of 3 Gy each fraction.

On C1D15, subjects will receive nivolumab 3 mg/kg IV. Thereafter, nivolumab administration will continue once every 2 weeks.

On C2D1, subjects will receive ipilimumab 1 mg/kg IV. Thereafter, ipilimumab administration will continue once every 6 weeks.

#### **Surgical Study Cohort:**

Two weeks following first doses of nivolumab and ipilimumab, all subjects will undergo craniotomy and tumor re-resection (C1D-15).

On C1D1, all surgical study subjects will receive a second dose of nivolumab

On C1D8, seven days after the 2nd nivolumab dose and 3 weeks after craniotomy, all surgical study subjects will begin HFRT to a total dose of 45 Gy, given in 15 consecutive fractions of 2.6 Gy each fraction.

On C1D15, subjects will receive nivolumab 3 mg/kg and ipilimumab 1 mg/kg IV. Thereafter, nivolumab administration will continue once every 2 weeks and ipilimumab administration will continue once every 6 weeks.

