### **Study Procedures:**

After screening procedures and registration, within 6 weeks of the first diagnostic surgery for glioblastoma, all subjects will initiate study treatment with one dose of nivolumab 3 mg/kg and one dose of ipilimumab 1mg/kg.

- Patients in the **Safety Lead-In/Main Study Cohort** will begin hypofractionated radiotherapy (HFRT) within 1 week of first nivolumab and ipilimumab dose.
- Patients in the **Surgical Study Cohort** (opens once Safety Lead-In completed) will undergo craniotomy and tumor re-resection within 2 weeks from the first dose of nivolumab and ipilimumab and begin HFRT 3 weeks following surgery

All subjects will receive HFRT to a total dose of 45 Gy, given in 15 consecutive fractions of 3 Gy each fraction.

All subjects will continue to receive nivolumab 3 mg/kg IV every 2 weeks and ipilimumab 1 mg/kg every 6 weeks from day of first nivolumab and ipilimumab administration. One treatment cycle will be defined as 42 days (6 weeks), corresponding to 3 doses of nivolumab and one dose of ipilimumab. Nivolumab and ipilimumab administration will continue for 2 years or until progression of disease, unacceptable toxicity, death, or another protocol criterion for subject withdrawal is met, whichever comes first.

Subjects will be evaluated every 8 weeks with radiographic imaging to assess response to treatment. The primary efficacy endpoint will be overall survival at 1 year. Disease assessments on study will be made using the Response Assessment for Neuro-Oncology (RANO) criteria. However, non-traditional Immunotherapy Response Assessment for Neuro-Oncology (iRANO) criteria may be considered for patient management. Adverse events will be monitored throughout the trial and graded in severity according to the guidelines outlined in the NCI Common Terminology Criteria for Adverse Events (CTCAE) version 4.03.

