### **5.2.2 Radiation Therapy**

RT must be provided at the study site (NYUSoM).

On Day 8 of Cycle 1 (7 days after initiation of study drugs), all subjects will begin HFRT to a total dose of 45 Gy, given in 15 fractions of 3 Gy.

CONFIDENTIAL

This material is the property of the NYU School of Medicine. Do not disclose or use except as authorized in writing by the study sponsor

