### 6.1.3 Surgical Study Cohort

The Surgical Study Cohort will open, once the Safety Lead-In in the Main Study Cohort is completed. We will use a single-stage design and enroll a total of 16 patients

After all screening, registration and baseline procedures have been completed as detailed on the **Schedule of Events (Appendix 1)**, subjects will begin study treatment as below:

CONFIDENTIAL

This material is the property of the NYU School of Medicine. Do not disclose or use except as authorized in writing by the study sponsor

On C1D-29, all subjects will initiate study treatment with one dose of nivolumab IV (3 mg/kg) followed by one dose of ipilimumab IV (1 mg/kg).

On C1D-15, all subjects in this cohort will undergo craniotomy and tumor re-resection.

On C1D1, all subjects will receive nivolumab IV (3 mg/kg)

On C1D8, all subjects will begin radiotherapy (RT) to a total dose of 45 Gy, given in 15 consecutive fractions of 3 Gy each fraction.

On C1D15, subjects will receive nivolumab 3 mg/kg and ipilimumab 1 mg/kg IV. Thereafter, nivolumab administration will continue once every 2 weeks and ipilimumab administration will continue once every 6 weeks.

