#### 6.5.4 Cycle 1, Day 8 (C1D8) – Begin of Radiation Therapy

Within 3 weeks (+/- 3 days) from craniotomy and tumor re-resection (i.e. Cycle 1, Day 8), the subject will initiate **RT**. RT must be provided at the study site (NYUSoM). Technical details for radiation therapy are provided in Section 5.2.2.

- Prior to initiating radiation therapy on C1D8, adverse event assessment, a symptom-directed physical exam and limited vital signs (temperature, resting blood pressure, pulse, and respiration rate) must be performed.
- All subjects will receive HFRT to a total dose of 45 Gy given as 3 Gy per fraction over 15 fractions. RT must begin 3 weeks (+/- 3 days) after craniotomy and tumor re-resection (i.e., Day 8 of Cycle 1).

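### Section 3.1.3 gives the surgical cohort 45 Gy in 15 fractions of 2.6 Gy, which multiplies to 39 Gy and is at odds with every other statement of the fraction size

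*Combined protocol and SAP*

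**What the plan says.** The surgical-cohort part of Section 3.1.3 (General Overview Study Procedures) says that on C1D8 "all surgical study subjects will begin HFRT to a total dose of 45 Gy", "given in 15 consecutive fractions of 2.6 Gy each fraction".

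The other statements that cover this cohort give a different fraction size:

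- Synopsis, Study Procedures: "All subjects will receive HFRT to a total dose of 45 Gy, given in 15 consecutive fractions of 3 Gy each fraction". The synopsis entry on investigational products gives the same schedule.
- Section 5.2.2 (Radiation Therapy): "all subjects will begin HFRT to a total dose of 45 Gy, given in 15 fractions of 3 Gy".
- Section 6.1 (Overall Study Design): the same schedule, for all subjects.
- Section 6.1.3 (Surgical Study Cohort): "given in 15 consecutive fractions of 3 Gy each fraction", for a total of 45 Gy.
- Section 6.5.4 (surgical cohort, C1D8): "All subjects will receive HFRT to a total dose of 45 Gy given as 3 Gy per fraction over 15 fractions".
- Appendix 2 (surgical Schedule of Events): both the table row and footnote 24 give 15 fractions of 3 Gy, 45 Gy in total.

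Within Section 3.1.3 itself, the main-cohort sentence reads "to a total dose of 45 Gy, given in 15 consecutive fractions of 3 Gy each fraction". No section sets out a separate fractionation for the surgical cohort or gives a reason for one.

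**The concern.** One sentence states a total, a number of fractions and a fraction size, and the three do not agree. A reader cannot tell from the sentence which of them is wrong.

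It is not safe to assume that everyone will pass over it as a slip. The odd figure stands only in the cohort-specific sentence, directly after a main-cohort sentence with 3 Gy, so it can look like a deliberate difference between cohorts. Nor is it far from other figures in the document. Section 1.1.6 cites a trial of 40 Gy in 15 fractions, which is 40/15 = 2.67 Gy each, and the text under Table A2 limits the optic structures to less than 267 cGy per fraction. The documents do not show where 2.6 came from.

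At stake is what up to 16 surgical subjects receive. If some were planned from Section 3.1.3 and others from Section 6.5.4, the cohort would have been treated with two different radiation doses.

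**Working it through.** **Inputs.** From the surgical sentence in Section 3.1.3: total 45 Gy, n = 15 fractions, d = 2.6 Gy per fraction. From the other sections listed: total 45 Gy, n = 15, d = 3 Gy.

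**Step 1: total dose = n x d.**

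| Source | n x d | Stated total | Difference |
|---|---|---|---|
| Synopsis, 5.2.2, 6.1, 6.1.3, 6.5.4, Appendix 2 | 15 x 3 = 45 Gy | 45 Gy | 0 |
| 3.1.3, surgical cohort | 15 x 2.6 = 39 Gy | 45 Gy | 6 Gy; 6/45 = 13.3% |

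**Step 2: can rounding explain it?** No. A total of 45 Gy in 15 fractions needs 45/15 = 3.0 Gy per fraction. A total of 45 Gy at 2.6 Gy needs 45/2.6 = 17.3 fractions, which is neither 15 nor a whole number.

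**Step 3: the protocol's own equivalent doses.** The pituitary paragraph in Section 5.2.2.2 gives equivalent doses at 2 Gy per fraction of 54 Gy (alpha/beta 3) and 49 Gy (alpha/beta 10). The formula is n x d x (d + ab)/(2 + ab), where ab is alpha/beta.

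- d = 3, ab = 3: 45 x 6/5 = 54.0 Gy
- d = 3, ab = 10: 45 x 13/12 = 48.75 Gy, printed as 49
- d = 2.6, ab = 3: 39 x 5.6/5 = 43.7 Gy
- d = 2.6, ab = 10: 39 x 12.6/12 = 40.95 Gy

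The protocol's figures are reproduced with 15 x 3 Gy and not with 15 x 2.6 Gy.

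**Step 4: the planning limits.** Table A1 takes 45 Gy as the prescription dose. Outside areas of overlap with organs at risk, it classes coverage of less than 90% of the planning target volume at 45 Gy as an unacceptable deviation. Assume that Table A1's 110% ceiling on the maximum dose were carried over to a 39 Gy plan. The maximum would then be 1.10 x 39 = 42.9 Gy, so no part of the target would reach 45 Gy and the plan would fail.

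Steps 3 and 4 show which parts of the document agree with one another. They do not establish which dose the sponsor intends.

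**Step 5: which surgical-cohort outcomes could be touched.** Section 6.1.3 puts the first doses on C1D-29, the re-resection on C1D-15 and the start of radiotherapy on C1D8. Section 6.5.2 has the research tumor specimen taken during the re-resection, about three weeks before radiotherapy begins (Section 6.5.4).

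- T-cell pathway induction, the only surgical endpoint with a sample-size calculation (Section 7.2.3): not affected. This assumes that induction is measured on the re-resection specimen, the only post-dose tumor tissue scheduled for every surgical subject.
- Safety up to the start of radiotherapy: not affected.
- Safety after radiotherapy, part of the primary objective in Section 3.2: affected if doses differed between subjects.
- OS, PFS and radiographic response, secondary in Section 3.3: affected if doses differed between subjects.

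No power, alpha or sample-size figure depends on the fraction size.

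**The case against.** The strongest case on the other side is that this is one wrong number in an overview, with little chance of reaching a patient. Section 3.1.3 closes by referring the reader to the study procedures and the Schedule of Events for specifics. The sections a treating team would use agree with one another, and Section 6.5.4 refers to Section 5.2.2 for technical details. Radiotherapy is given at the single study site. Table A1 and the brainstem limit are built on a 45 Gy prescription, so a 39 Gy plan would probably be stopped at planning. Section 5.2.2.7 also has the treatment records and dose distributions sent to the overall Principal Investigator.

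Most of this stands, and it makes delivery at 2.6 Gy unlikely. It does not remove the contradiction, and two of the safeguards have gaps for this cohort. The closing reference in Section 3.1.3 names Appendix 1, which is the main cohort's schedule; the surgical schedule is Appendix 2. Section 5.2.2 describes Day 8 as seven days after study drugs begin, which does not fit subjects whose first dose is on C1D-29. A reader could therefore take Section 5.2.2 as main-cohort text and rely on the surgical sentence in Section 3.1.3.

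Two stronger readings are tempting. A reader might infer that the surgical cohort is meant to receive a lower dose. The documents do not support that: no section describes such a difference, and the same sentence keeps the 45 Gy total. A reader might also infer that the discrepancy makes the cohort's results uninterpretable. That is not supported either. The pathway-induction tissue precedes radiotherapy, and the later outcomes suffer only if subjects were in fact treated differently.

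**Conclusion.** The point holds, within limits. The surgical-cohort sentence in Section 3.1.3 contradicts itself by 6 Gy (13.3% of the stated total), and its fraction size conflicts with every other statement of the study's schedule. This rests on multiplication and on the text as printed; the sentence is running prose in the current treatment description.

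The weight comes from the subject matter, not from the likelihood of harm. An inconsistent radiation dose in a protocol should be corrected however improbable it is that anyone acts on it. The statistical reach is narrow and conditional: post-radiotherapy safety and the secondary efficacy estimates, and only if the fraction size delivered varied between subjects.

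**What to change.** Reconcile the surgical-cohort sentence in Section 3.1.3 with Sections 5.2.2, 6.1, 6.1.3 and 6.5.4 and with Appendix 2, so that fraction size, number of fractions and total dose agree everywhere. The sponsor and the responsible radiation oncology team must confirm the intended figures; this review does not choose between them.

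The cost is a one-line protocol correction with no effect on sample size or analysis. If any surgical subject has already been treated, the radiotherapy summaries required by Section 5.2.2.7 will show what was delivered, and the report should state it.
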